#### 10.6.2 Medical Safety Monitor

All SAEs will be reported per local IRB policy. This study will utilize a medical safety monitor named in the Independent Medical Monitoring Charter. The Medical Safety Monitor will provide the medical coverage needed when serious or unexpected AEs occur.

#### 10.6.3 Stopping Rules

The Medical Safety Monitor will act in an advisory capacity to monitor the safety of subjects on a routine basis throughout the trial. The drug safety and pharmacovigilance group at Ultragenyx will review SAEs and may provide advice in any determination of whether study enrollment should be paused or if the study should be halted.

Individual subjects who experience any unexpected and possibly, probably, or definitely drug-related SAEs that represent a change in the nature or an increase in frequency of the serious event from their prior medical history will be assessed as to whether the subject will continue on the study.

Should unexpected and possibly, probably, or definitely drug-related SAEs occur, a full clinical evaluation will be performed by the medical safety monitor, the principal investigator, and drug safety and pharmacovigilance group in order to make a decision regarding what actions to take, including whether to recommend stopping the study and informing the IRB.

#### 10.6.4 Safety Report

Copies of all reports will be stored in the Study File. All SAEs will be reported to the FDA, the CCHCS IRB, and the supporting institution, Ultragenyx, Inc.

#### 10.6.4 Protocol Violations

Protocol violations are events that are inconsistent with the protocol to the extent of impacting the study outcome and / or GCP guidelines. Protocol violations include but are not limited to violations regarding consent and IRB issues, administration of wrong treatment and incorrect laboratory testing. Protocol violations should be reported per the CCHCS RAO policy.

### 11.0 STATISTICAL CONSIDERATIONS

#### 11.1 *Safety Analysis*

Safety data will be reviewed annually or more frequently, as needed, by another physician investigator familiar with the disorder and treatment. For the safety analysis, the numbers (frequency) and incidence rates of AEs and SAEs will be summarized during exposure to triheptanoin throughout the study. The analyses of safety will include all subjects who receive any triheptanoin during the study and provide any post-treatment safety information. All AEs will be coded using the Medical Dictionary for Regulatory Activities (MedDRA). The incidence and frequency of AEs will be summarized by System Organ Class (SOC), Preferred Term (PT), relationship to study drug, and severity. A by-subject listing will be provided for those subjects who experience a SAE, including death, or experience an AE associated with early withdrawal from the study or study drug treatment.

Clinical laboratory data will be summarized by the type of laboratory test. The frequency and percentage of subjects who experience abnormal clinical laboratory results (i.e., outside of reference ranges) and/or clinically significant abnormalities after study drug administration will be presented for each clinical laboratory measurement. For each clinical laboratory measurement, descriptive statistics will be provided for Baseline and all subsequent scheduled visits during which laboratory measurements were obtained. Changes from Baseline to the treatment visits will also be provided. Descriptive statistics of vital signs and concomitant medications will be provided in a similar manner.

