## **4.0 SELECTION AND ENROLLMENT OF SUBJECTS**

### **4.1 Inclusion Criteria**

Individuals eligible to participate in this study must meet all of the following criteria:

- 1) Patients with GLUT1 DS by physician diagnosis
- 2) Males and females, aged 1 to 50 years
- 3) Allowed to be on concomitant AEDs
- 4) Patients are able to tolerate triheptanoin if they have been (or are currently being) treated with this medication
- 5) Must, in the opinion of the investigator, be willing and able to comply with study procedures and schedule
- 6) Provide written assent (if appropriate) and written informed consent by a Legally Authorized Representative (LAR) after the nature of the study has been explained, and prior to any research-related procedures
- 7) Sexually active subjects must be willing to use an acceptable method of contraception while participating in the study
- 8) Females of childbearing potential must have a negative pregnancy test at Screening and be willing to have additional pregnancy tests during the study

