## 5.3 Duration of Treatment

Duration of the initial treatment is 4 years with an additional one-year extension period.

Triheptanoin will be provided to the patient by the CCMC Investigational Drug Service pharmacy (IDS pharmacy) during visit 1 and at all scheduled clinic visits. In lieu of dispensation at time of study visit, the IDS pharmacy may choose to ship either a 3-month or 6-month supply to patients, as prescribed by the PI.

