#### 5.4.1 Schedule A

- Subjects previously treated with triheptanoin will continue to dose at approximately 35-40% of total daily calories (~1-4g/kg/day, depending on age).
- The visit schedule will be: Visit 1 (day 1), Visit 2 (13 weeks), Visit 3 (26 weeks), Visit 4 (52 weeks), Visit 5 (Year 2, week 26), Visit 6 (Year 2, Week 52), Visit 7 (end of Year 3), Visit 8 (end of Year 4), and Visit 9 (end of Year 5), with telephone follow-up between visits, as needed. (Table 1)

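### Section 11.1 names no safety split by prior exposure, so change from Baseline mixes on-drug and pre-drug references and overall AE incidence can understate early tolerability events

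*Combined protocol and SAP*

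**What the plan says.** Safety, judged by AE rates and laboratory values, is the primary objective (section 1.1). Section 11.1 sets out the analysis:

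- Analysis set: "The analyses of safety will include all subjects who receive any triheptanoin during the study and provide any post-treatment safety information".
- AE window: "the numbers (frequency) and incidence rates of AEs and SAEs will be summarized during exposure to triheptanoin throughout the study".
- AE breakdowns: "The incidence and frequency of AEs will be summarized by System Organ Class (SOC), Preferred Term (PT), relationship to study drug, and severity".
- Laboratory data: descriptive statistics at Baseline and each scheduled visit, and "Changes from Baseline to the treatment visits will also be provided". Baseline is not defined.
- Vital signs: "Descriptive statistics of vital signs and concomitant medications will be provided in a similar manner".

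Neither section 11.1 nor any other section asks for safety results by schedule, prior exposure, drug status at entry or time since first dose.

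The trial enrols two kinds of subject, up to 50 in total, with no planned split (sections 3.1 and 3.2). For prior users, inclusion criterion 4 in section 4.1 requires that "Patients are able to tolerate triheptanoin if they have been (or are currently being) treated with this medication", and section 5.4.1 says: "Subjects previously treated with triheptanoin will continue to dose at approximately 35-40% of total daily calories". Naive subjects start the drug on study and titrate over two weeks (sections 5.4.2 and 5.4.3). They also have a Day 14 phone visit with AE review in Table 2, which Table 1 does not have.

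Under section 5.4.4.2 and both event tables, blood is drawn at Screening and next at Week 13, with no Day 1 sample. Vital signs are taken at Screening and at Visit 1.

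**The concern.** The two groups enter at different points of exposure. For a continuing subject, Screening is a value on triheptanoin; for a naive subject, it is a value before triheptanoin. One summary of change from Baseline then averages change during continued use with change after starting. By contrast, the efficacy analysis in section 11.2 is tied explicitly to the period before triheptanoin.

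For AEs, prior users are selected for tolerance, and whatever they experienced on first starting lies outside the on-study window. The overall incidence describes on-study experience correctly. It is not the incidence a patient starting the drug would face.

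Both outputs therefore depend on an enrolment mix that the protocol does not fix, and a reader could not separate starting triheptanoin from continuing it. No hypothesis is tested, so what is at stake is interpretation of the primary objective, not error control.

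**Working it through.** The plan states no expected AE rate, effect size or enrolment mix, so there is no figure of its own to reproduce. The total of 50 comes from section 3.2. The mix, r, RR and k below are assumptions.

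**1. Which reference each group has.**

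| | Screening laboratory value | Vital signs at Screening or Visit 1 |
|---|---|---|
| Continuing on drug (section 5.4.1, Table 1) | on drug | on drug |
| Naive (section 5.4.2, Table 2) | pre-drug | pre-drug |

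The vital-sign column follows because the table footnotes place vital signs at the start of each visit, and section 5.3 says: "Triheptanoin will be provided to the patient by the CCMC Investigational Drug Service pharmacy (IDS pharmacy) during visit 1". Choosing Visit 1 instead of Screening as Baseline would not remove the mixture.

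**2. Mean change from Baseline.** Let d be the true mean change on drug, equal in both groups, with no other trend. Let r be the share of d already present at Screening in on-drug subjects. Off-drug subjects show d and on-drug subjects show d(1 − r), so

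share of d shown = [n_off + n_on × (1 − r)] / 50.

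With 30 on drug: r = 1 gives 20/50 = 40%; r = 0.5 gives (20 + 15)/50 = 70%; r = 0 gives 50/50 = 100%.

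| On drug, of 50 | r = 1 | r = 0.5 | r = 0 |
|---|---|---|---|
| 10 | 80% | 90% | 100% |
| 30 | 40% | 70% | 100% |
| 40 | 20% | 60% | 100% |

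The formula holds for means, not medians.

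**3. AE incidence.** Let RR be the ratio of incidence in prior users (n_A) to that in naive subjects (n_B). Then

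overall / naive = [n_B + n_A × RR] / 50.

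With n_A = 30 and n_B = 20: RR = 0.25 gives 27.5/50 = 0.55; RR = 0.5 gives 35/50 = 0.70; RR = 1 gives 1.00; RR = 1.5 gives 65/50 = 1.30. Understatement needs RR below 1. Criterion 4 makes that plausible for early tolerability events. The documents give no timing for gastrointestinal events, although the titration guide in section 5.4.3 anticipates tolerability problems. For late or cumulative events, including weight gain, nothing fixes the sign.

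**4. Secondary: time since first dose.** This applies only if incidence rates are person-time rates. To Week 13 is 13/260 = 5% of follow-up for a 5-year completer (5 × 52 weeks). If the early rate is k times the later rate, whole-study rate / early rate = (0.05k + 0.95)/k, which is 1.00, 0.525, 0.24 and 0.145 for k = 1, 2, 5 and 10.

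**5. Precision lost by splitting.** The one-sided 95% upper limit after zero events is 1 − 0.05^(1/n): 5.8% at n = 50, 13.9% at n = 20 and 25.9% at n = 10.

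**The case against.** The strongest reply is that silence is not a rule. Section 11.1 defines one analysis set and lists breakdowns; it does not forbid others. Schedule is settled at enrolment, so a later split by schedule would not be data-driven. The study is open-label and descriptive. Percentages outside reference ranges and the by-subject listings of SAEs and withdrawals do not use Baseline, so they escape the problem. All of this stands, and it limits the severity. It does not remove the point: followed as written, the plan delivers only overall summaries of the two measures named in the primary objective, and the unaffected outputs show neither non-serious start-up events nor a laboratory shift from before treatment.

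The illustrative figures also rest on assumptions whose ranges include no effect (r = 0, RR = 1, k = 1) and, for AEs, reversal (RR = 1.5). That is correct; the figures show sensitivity to the mix and are not estimates.

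Two further inferences are tempting. A reader might take the heading over Table 1's footnotes, which covers current or previous users, as evidence that lapsed users will enrol. The same heading stands over the footnotes to the naive-subject table, so it carries no weight; Table 1's title and section 5.4.1 describe continued dosing. Only criterion 4 leaves lapsed users possible. A reader might also infer from step 4 that early events are necessarily diluted within Schedule B. An incidence proportion is not diluted by longer follow-up, and section 11.1 does not define its rates as person-time.

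**Conclusion.** The point holds as a should-fix matter of interpretation. It is firmest for laboratory change from Baseline, where the mixture of references follows from the sampling schedule itself; only its size depends on assumptions (the mix, r, and an equal mean effect with no other trend). The same mixture applies to vital-sign changes if these are summarised in the same way. For AEs the conclusion is narrower: overall incidence can understate early tolerability events relative to starting the drug.

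A reader might infer that the plan hides harm generally, or that overall AE rates will be too low. The documents do not support that: they give no mix, rates or effect size, and the direction for late events is unknown.

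**What to change.** In section 11.1:

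1. Present AE, SAE, laboratory and vital-sign summaries by triheptanoin status at Screening (on or off drug, from the Screening medication record in Tables 1 and 2) and by Schedule A and B, beside the overall totals. The status flag keeps any prior user who is off drug at entry from being counted with continuing subjects.
2. Report change from Baseline separately for the on-drug and off-drug groups. Interpret only the off-drug group as change from a pre-triheptanoin value, with two caveats: some may have been on ketogenic diet at Screening, since section 5.4 lets the screening period be waived for such patients, and growth can move values over up to five years.
3. As a secondary table, for everyone who starts or restarts on study (Schedule B plus any off-drug prior users), summarise AEs by time since first on-study dose, for example to Week 13 and later. Say whether incidence rates are person-time rates; the table matters mainly if they are.
4. State whether Screening or Visit 1 is Baseline for vital signs.
5. Keep out-of-range percentages for all subjects.

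The AE columns should not be read as a clean comparison of groups, because Schedule B has the extra Day 14 AE contact.

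The cost is SAP wording, extra columns and one table, with no new visit or sample. Item 3 needs AE onset dates; that these are recorded is an assumption, since section 10.1 refers to a Data Dictionary for the variable list. The statistical price is the loss of precision shown in step 5 of the working; the pooled totals are kept.

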## **An Open-Label Trial of Triheptanoin in Patients with Glucose Transporter Type-1 Deficiency Syndrome (GLUT1 DS)**

### **1.0 GOALS AND OBJECTIVES**

- 1.1 The primary objective of the study is:
- To evaluate the safety of triheptanoin via adverse event rates and laboratory values.
- 1.2 The secondary objective of the study is:
- To evaluate the long-term efficacy of triheptanoin as measured by the change in seizure frequency from historical baseline.

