Triheptanoin has been found to be effective in 4 of 7 animal models of epilepsy. In the corneal kindling chronic model, triheptanoin delayed development of kindled seizures in a dose-dependent manner, but did not protect against fully kindled seizures. In the chronic model of PTZ (pentylenetetrazole) in pilocarpine-status epilepticus, triheptanoin partially reversed the lowered PTZ threshold for tonic seizures but not clonic seizures in the chronic stage. In the maximal electroshock threshold model, triheptanoin increased the seizure threshold. In the genetic mouse model of generalized epilepsy due to the GABA-A-gamma2(R43Q) mutation, triheptanoin halved the time spent in seizures and reduced the frequency of seizures caused by insulin-induced hypoglycemia. However, triheptanoin was not effective in the fluorothyl, pentylenetetrazole nor 6Hz models. The efficacy of triheptanoin in some but not all animal models of epilepsy is similar to that found with other AEDs.

In toxicology studies, there were no toxic effects on animal growth, lipid digestibility, clinical chemistry parameters, or the histopathology of liver, kidney and small intestine in rats fed for 9 months with triheptanoin at levels that replaced up to 50% of the standard soybean oil in rodent chow. Hepatic steatosis and alterations in intestinal villi were the only findings observed in a single 9 month repeat dose oral rat toxicology study. The findings may be due to the effect of extreme fat overload compared with the normally low fat intake in rats (~10-fold normal fat intake) and the efficient direct absorption, non-bile-dependent of triheptanoin and metabolites. This adverse effect has not been observed in previous human clinical trials in which FAOD patients have shown the opposite finding, a reduction in hepatomegaly/steatosis, with triheptanoin treatment.

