### 3.2 Number of Subjects Planned

The study will enroll up to 50 subjects in total.

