### **4.2 Exclusion Criteria**

Individuals who meet any of the following exclusion criteria will not be eligible to participate in the study:

- 1) Patients and their Legally Authorized Representatives (as appropriate) not willing or able to give written or verbal assent or written informed consent.
- 2) Concomitant administration of a ketogenic diet for the treatment of GLUT1 deficiency at time of study drug initiation
- 3) Concomitant administration of valproic acid
- 4) In the Investigator's opinion, the patient may not be compliant
- 5) Pregnant or breastfeeding an infant at screening
- 6) Has a concurrent disease or condition, or laboratory abnormality that, in the view of the Investigator, places the subject at high risk for adverse events, or introduces additional safety concerns
- 7) History of or current suicidal ideation, behavior and attempts
- 8) Patient qualifies for any other clinical trial designed to progressively evaluate the safety and efficacy of triheptanoin as approved by the FDA under a separate IND which is open at Cook Children's

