##### 5.4.4.2 Laboratory

Blood samples will be collected for CBC, Chem-7, ALT/AST, at Screening, Week 13, and every six months through the end of year 2, and annually thereafter for all subjects.

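### The planned percentage of subjects with out-of-range laboratory results ignores the Screening value, direction and size, so it mixes chance and pre-existing abnormality with any drug effect

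*Combined protocol and SAP*

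**What the plan says.** The primary objective (Section 1.0) is "To evaluate the safety of triheptanoin via adverse event rates and laboratory values". The laboratory analysis is in Section 11.1. Its one categorical summary is "The frequency and percentage of subjects who experience abnormal clinical laboratory results", with abnormality described as "abnormal clinical laboratory results (i.e., outside of reference ranges) and/or clinically significant abnormalities after study drug administration", presented for each laboratory measurement. Section 11.1 does not require an in-range Screening value or a worsening from it. It sets no direction, grade, multiple of a limit or confirmation rule, and it does not define clinical significance.

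The same section also plans descriptive statistics at Baseline and at each scheduled visit, and changes from Baseline.

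Blood is drawn "at Screening, Week 13, and every six months through the end of year 2, and annually thereafter for all subjects" (Section 5.4.4.2). The late visits are "Visit 7 (end of Year 3), Visit 8 (end of Year 4), and Visit 9 (end of Year 5" (Section 5.4.1, and the same in 5.4.2). Tables 1 and 2 place laboratory tests at Screening and at Visits 2 to 9, but not at Visit 1.

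On entry, Section 4.2 excludes only a "laboratory abnormality that, in the view of the Investigator, places the subject at high risk for adverse events" or that raises further safety concerns, so other abnormalities may come in. Section 4.1 allows concomitant antiepileptic drugs.

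**The concern.** With no control arm, nothing in the trial absorbs the background rate of out-of-range results. Three things other than the drug feed the percentage as written.

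- A subject who was out of range at Screening and stays there is counted as abnormal after study drug.
- Each further draw gives a stable subject another chance to stray just past a limit, so the figure depends on length of follow-up. Subjects who leave early and subjects who complete five years are not comparable.
- A result barely beyond the limit and a several-fold rise each count as one subject.

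The reader of the final report would not be able to say how much of the percentage is new, how much is large, and how much would have been there without treatment. This matters most for liver tests. In a nine-month rat study "Hepatic steatosis and alterations in intestinal villi were the only findings observed" (Section 2.2.1), and a clear liver readout in humans is the natural answer to that finding.

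**Working it through.** The plan states no expected abnormality rate, so there is no figure of its own to reproduce. The check asks what the rule would return if triheptanoin had no effect.

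**Inputs from the documents**
- On-drug draws: Weeks 13, 26, 52, 78 and 104, and the ends of Years 3, 4 and 5, which makes k = 8 (Sections 5.4.1, 5.4.2 and 5.4.4.2; Tables 1 and 2). A separate termination draw would make 9.
- Sample size: "The study will enroll up to 50 subjects in total" (Section 3.2).

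**Assumptions, not in the documents**
- 5% of values fall outside the range at each draw (2.5% on each side), as for a central 95% reference range in a similar population.
- All k draws are completed.
- Repeated values in one subject are normal with common correlation ρ, varied from 0 to 0.9.

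**Formulas**
- Independent draws: P(ever outside) = 1 − 0.95^k. For k = 8: 1 − 0.95^8 = 0.337. High side only: 1 − 0.975^8 = 0.183.
- Correlated draws: for a subject with random level b (standard normal), the chance that one draw is in range is p(b) = Φ((1.96 − √ρ·b)/√(1−ρ)) − Φ((−1.96 − √ρ·b)/√(1−ρ)). Then P(ever outside) = 1 − E[p(b)^k], by numerical integration over b. For the high side only, drop the second term.
- New abnormality among subjects in range at Screening: E[p(b)·(1 − p(b)^k)] / 0.95.

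**Results, no drug effect**

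| Count | ρ = 0 | 0.5 | 0.8 | 0.9 |
|---|---|---|---|---|
| Ever outside, 8 draws | 33.7% | 25.0% | 15.7% | 11.9% |
| Ever high, 8 draws | 18.3% | 12.5% | 7.9% | 6.0% |
| Ever outside, 5 draws (to Year 2) | 22.6% | 18.3% | 12.7% | 10.2% |
| Ever outside, 3 draws (to Week 52) | 14.3% | 12.5% | 9.8% | 8.4% |
| Ever outside, 9 draws | 37.0% | 26.9% | 16.5% | 12.4% |
| New only, among those in range at Screening, 8 draws | 33.7% | 23.1% | 12.2% | 7.7% |

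With 50 completers, the first row is 0.337 × 50 ≈ 17 subjects per analyte at ρ = 0, 0.157 × 50 ≈ 8 at ρ = 0.8, and 0.119 × 50 ≈ 6 at ρ = 0.9.

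**Share already abnormal at Screening.** At ρ = 0.8, 15.7% of all subjects are flagged. Of all subjects, 11.5% are flagged and were in range at Screening (0.122 × 0.95 ≈ 0.115). So (15.7 − 11.5)/15.7 ≈ 27% of those flagged were already out. This is the share in a population resembling the reference population. Disease- or drug-related abnormality at entry is not modelled and would raise it.

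**What a Screening condition alone achieves.** At ρ = 0.8 it lowers the percentage from 15.7% to 12.2%, and at ρ = 0 it changes nothing. Most chance flags remain, so a size threshold is needed as well.

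**The case against.** The strongest reply is that Section 11.1 is descriptive. It tests nothing, sets no decision threshold, and does not rely on this percentage alone. By-visit statistics and changes from Baseline are planned, clinically significant abnormalities are also counted, a physician reviews safety data at least annually, and Section 10.6.1 calls for review of laboratory trends. All of this stands, and it limits the harm. But by-visit summaries do not show which subjects moved from in range to out of range, and the planned by-subject listing covers SAEs and AE-related withdrawals, not laboratory outliers.

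It is also fair that the size is assumed. The 5% rate, full follow-up and the correlations are not in the documents, and zero correlation within one person over five years is an extreme. The 16% is therefore not a floor. The accumulation over draws is itself an inference: Section 11.1 refers to results after study drug administration and does not say ever or worst value.

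Four stronger readings are tempting but not supported.

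- A reader might infer that large rises will vanish in a mean change. Section 11.1 does not say mean; descriptive statistics may include the median and the maximum, and a maximum would show a large rise.
- A reader might multiply across the panel and conclude that nearly every completer will be flagged for something. No any-analyte percentage is planned, and the multiplication would treat related tests such as ALT and AST as independent.
- A reader might conclude that a liver effect could not be told from noise. The other planned summaries and reviews argue against that. Section 2.2.1 also reports no toxic effect on clinical chemistry in rats, offers fat overload as an explanation, and says the finding was not seen in earlier human trials.
- A reader might attribute the 16-34% to abnormality from disease or antiepileptic drugs. The figure contains none; any such excess comes on top.

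**Conclusion.** The concern holds in a limited form. The stated rule is a count of subjects beyond a reference limit that ignores the Screening value, direction and size, so in a single-arm trial it does not isolate what changed on treatment. Given 5% outside per draw, 8 completed draws and no drug effect, it would flag about 16-34% of subjects per analyte for correlations from 0.8 down to 0, and about 12% at 0.9. High values alone give about 8-18% over the same 0.8 to 0 range. Shorter follow-up lowers these figures, and a raised background rate increases them. The weakness of the rule does not depend on the exact value. It is a reporting defect in part of the primary objective, partly offset by the other summaries, and cheap to put right.

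**What to change.** In Section 11.1, replace the percentage, or accompany it, with the following.

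1. A shift table for each analyte: low, normal or high at Screening against each scheduled visit and against the worst on-treatment value. Count new abnormalities among subjects in range at Screening, and show the number of draws behind each percentage.
2. For liver tests, the number of subjects above fixed multiples of the upper limit, or of their own Screening value if that was already raised. Set the multiples before the data are analysed. This part is essential, because the Screening condition alone leaves most chance flags.
3. Both sets of tables separately for Schedule A and Schedule B. Schedule A subjects continue triheptanoin, so their Screening value may be on-drug and is not a pre-treatment baseline. Counting only new abnormalities in that group could leave out ones the drug had already caused.

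Reconcile the laboratory panel as well. Section 5.4.4.2 lists CBC, Chem-7 and ALT/AST, while the footnotes to Tables 1 and 2 give a longer chemistry list that includes ALP, GGT and total bilirubin. Which liver tests can be tabulated depends on the answer.

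The cost is revised wording and a few more tables. If the longer panel is the one being run, no new samples are needed. The drawback is a smaller denominator for analytes often abnormal at Screening, made smaller still by the split by schedule with at most 50 subjects.
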